14.5.6 Exploratory Analyses

Any correlations between clinical, radiological, and PD outcomes will be evaluated.

15. Ethical Aspects

15.1 Local Regulations/Declaration of Helsinki

The investigator will ensure that this study fully adheres to the principles outlined in "Guideline for Good Clinical Practice" ICH Tripartite Guideline (January 1997) which has as its basis in the principles of the "Declaration of Helsinki" (2008) or with the laws and regulations of the country in which the research is conducted, whichever affords the greater protection to the public.

15.2 Informed Consent

It is the responsibility of the investigator, or a person designated by the investigator, to obtain written informed consent from each individual participating in this study after adequate explanation of the aims, methods, objectives and potential hazards of the study. It must also be explained to the subjects that they are completely free to refuse to enter the study or to withdraw from the study at any time for any reason. Appropriate forms for obtaining informed consent will be provided by the investigator.

If new safety information results in significant changes in the risk/benefit assessment, the consent form should be reviewed and updated if necessary. All subjects (including all those already treated) should be informed of the new information, given a copy of the revised form and asked to give their consent to continue in the study.

15.3 Independent Ethics Committee

This protocol and any accompanying material provided to the subject (such as Information Sheets) as well as any advertising or compensation given to the subject, will be submitted by the investigator to an Independent Ethics Committee. Approval from the committee must be obtained before starting the study and should be documented in a letter to the investigator specifying the date on which the committee met and granted approval.

Any modifications made to the protocol after receipt of Ethics Committee approval must also be submitted to the Ethics Committee in accordance with local procedures and regulatory requirements.

16. Conditions for Modifying the Protocol

Protocol modifications to ongoing studies must be made only after consultation between an appropriate representative of the sponsor and the investigator. Protocol modifications must be agreed in writing and signed by the investigator and sponsor.

All protocol modifications must be submitted to the appropriate Ethics Committee for information and approval in accordance with local requirements and Medsafe. Approval must be obtained before any changes can be implemented, except for changes necessary to eliminate an immediate hazard to study subjects, or when the change(s) involves only logisitical or administrative aspects of the study (eg, change in monitor(s) or telephone numbers.

17. Conditions for Terminating the Study

Both the sponsor and the investigator reserve the right to terminate the study at any time. Should this be necessary, both parties will arrange the procedures on an individual study basis after review and consultation. In terminating the study, the Sponsor and the investigator will assure that adequate consideration is given to the protection of the subject's interests.

The study can be terminated for (including, but not limited to) the following reasons:

- 1. A significant safety concern arising from either ongoing pre-clinical or clinical studies
- 2. Inability to recruit the required number of subjects to the study
- 3. Strategic termination of the development programme
- 4. Any other reason required by the sponsor or investigator

18. Study Documentation, CRFs and Data Handling

18.1 Investigator's Files/Retention of Documents

The investigator shall supply the sponsor on request with any required background data from the study documentation or clinic records. This is important when CRFs are illegible or when errors in data transcription are suspected. In case of special problems and/or governmental queries or requests for audit inspections, it is also necessary to have access to the complete study records, provided that subject confidentiality is protected.

The Investigator's File will contain the protocol/amendments, Case Report and Query Forms, Ethics Committee and Medsafe approval with correspondence, sample informed consent, drug records, staff curriculum vitae and delegation logs and other appropriate documents/correspondence, etc.

Clinical source documents will be defined in advance to record key efficacy/safety parameters independent of the CRF. They include subject clinical records, physician's and nurses' notes, original laboratory reports, ECGs, signed Consent Forms and subject screening and enrolment logs. The investigator must keep these two categories of documents on file for at least 15 years after completion or discontinuation of the study. After that time, the documents may be destroyed, subject to local regulations. Should the investigator wish to assign the study records to another party or move them to another location, the sponsor will be notified in advance.

The investigator shall supply the sponsor on request with any required background data from the study documentation or clinic records. This is important when CRFs are illegible or when errors in data transcription are suspected. In case of special problems and/or governmental queries or requests for audit inspections, it is also necessary to have access to the complete study records, provided that subject confidentiality is protected.

18.2 Confidentiality of Trial Documents and Subject Records

The investigator must be aware that subjects' anonymity will be maintained and that their identities are protected from unauthorised parties. On CRFs or other documents submitted to the sponsor, subjects should not be identified by name, but by an identification code. The investigator should keep a subject enrolment log relating codes to the names of subjects. The investigator should maintain documents not for submission to the sponsor, eg, subjects' written consent forms, in strict confidence.

18.3 Case Report Forms (CRFs)

It is the intent of this study to acquire study data via electronic format; however, should the electronic capture system be unavailable, paper CRF forms will be utilised.

Version 5

As part of the responsibilities assumed by participating in the study, the investigator agrees to maintain source documentation (eg, ECGs), to enter subject data into the electronic CRF (eCRF) as accurately as possible, and to respond to any reported discrepancies rapidly. eCRFs are accessed through the Trial Forms (Primorus Clinical Trials Ltd) remote data capture application, which allows for on-site data entry and data management. Site users can read from and write to the sponsor's database where the clinical data are collected. This provides immediate, direct data transfer to the database, as well as immediate detection of discrepancies, enabling site coordinators to resolve and manage discrepancies in a timely manner. Each person involved with the study at each site will have an individual identification code and password that allows for record traceability. Thus, the system, and subsequently any investigative reviews, can identify coordinators, investigators, and individuals who have entered or modified records.

For each subject enrolled, a CRF must be completed and signed a Principal Investigator or authorised delegate from the study staff. This also applies to records for those subjects who fail to complete the study (even during a pre-randomisation screening period if a CRF was initiated). If a subject withdraws from the study, the reason must be noted on the CRF. If the subject is withdrawn from the study because of a treatmentlimiting AE, thorough efforts should be made to clearly document the outcome.

All paper forms should be filled out using indelible ink and must be legible. Errors should be crossed out but not obliterated, the correction inserted and the change initialed and dated by the investigator and/or his/her authorised delegate. The investigator should ensure the accuracy, completeness, legibility and timeliness of the data reported to the sponsor in the CRFs and in all required reports.

18.4 Data Handling and Record Keeping

The full details of procedures for data handling will be documented in the Data Management Plan. Adverse events, medical history, and concurrent conditions will be coded using Medical Dictionary for Regulatory Activities (MedDRA). Drugs will be coded using the World Health Organization (WHO) Drug dictionary (WHODrug).

18.5 Assignment of Preferred Terms and Original Terminology

For classification purposes, preferred terms will be assigned by the sponsor to the original terms entered on the CRF, using the latest version of MedDRA (medical dictionary for regulatory activities terminology) for AEs and diseases and the WHODrug (World Health Organisation Drug dictionary) drug terms and procedures dictionary for treatments and surgical and medical procedures.

18.6 Study Centre Monitoring Visits

Monitoring visits to the study site will be made periodically during the study to ensure that all aspects of the protocol are followed. It is understood that the responsible monitor will contact and visit the investigator regularly and will be allowed, on request, to inspect the various records of the study (CRFs and other pertinent data) provided that subject confidentiality is maintained in accord with local requirements.

Source documents will be reviewed for verification of data recorded on the eCRFs. Source documents are defined as original documents, data, and records.

The investigator and his/her delegates agree to cooperate with the monitor to ensure that any problems detected in the course of these monitoring visits are resolved.

18.7 Quality Assurance and Regulatory Agency Audits

The study site also may be subject to quality assurance audits by the sponsor or designees. In this circumstance, the sponsor-designated auditor will contact the site in advance to arrange an auditing visit. The auditor may request to visit the facilities where laboratory samples are collected, where the medication is stored and prepared, and any other facility used during the study.

In addition, there is the possibility this study may be inspected by regulatory agencies (Medsafe), including those of foreign governments (eg, the US Food and Drug Administration [FDA], the United Kingdom Medicines and Healthcare products Regulatory Agency [MHRA]). If the study site is contacted for an inspection by a regulatory body, the sponsor should be notified immediately. The investigator and institution guarantee access to source documents by the sponsor or its designee (CRO) and by the IRB or EC or regulatory body.

19. Publication of Data and Protection of Trade Secrets

The results of this study may be published or presented at scientific meetings. If this is foreseen, the investigator agrees to submit all manuscripts or abstracts to the Sponsor at least 30 days prior to submission. This allows the sponsor to protect proprietary information and to provide comments based on information from other studies that may not yet be available to the investigator.

Any formal publication of the study in which input of the Sponsor's personnel exceeded that of conventional monitoring will be considered as a joint publication by the investigator and the appropriate sponsor personnel. Authorship will be determined by mutual agreement.

20. References

- 1. Fallon P. G., Alcami A., (2006) Pathogen-Derived Immunomodulatory Molecules. Future Immunotherapeutics? *Review TRENDS in Immunol 27* (10)
- 2. Gay N. J., Gangloff M. (2007) Structure and Function of Toll Receptors and Their Ligands, *Annu. Rev. Biochem.* (76).141-65
- Tomai M. A., Miller R. L., Lipson K. E., Vasilakos J. P., Woulfe S. L. (2006) Immune Response Modifiers. Imiquimod and Future Drugs for Modulating the Immune Response. Drug Discovery Today. *Therapeutic Strategies 3* (3)
- 5. Sirard J-C, Vignal C., Dessein R., Chamaillard M. (2007) Nod-Like Receptors: Cytosolic Watchdogs for Immunity Against Pathogens. *PLoS Pathogens Vol 3* (12)

Appendix 1 McDonald Criteria for Diagnosis of Multiple Sclerosis

| Clinical Presentation | Additional Data Needed |
|---|---|
| * 2 or more attacks (relapses) * 2 or more objective clinical lesions | None; clinical evidence will suffice (additional evidence desirable but must be consistent with MS) |
| * 2 or more attacks * 1 objective clinical lesion | Dissemination in space, demonstrated by: * MRI * or a positive CSF and 2 or more MRI lesions consistent with MS * or further clinical attack involving different site |
| * 1 attack * 2 or more objective clinical lesions | Dissemination in time, demonstrated by: * MRI * or second clinical attack |
| * 1 attack * 1 objective clinical lesion (monosymptomatic presentation) | Dissemination in space demonstrated by: * MRI * or positive CSF and 2 or more MRI lesions consistent with MS and Dissemination in time demonstrated by: * MRI * or second clinical attack |
| Insidious neurological progression suggestive of MS (primary progressive MS) | One year of disease progression (retrospectively or prospectively determined) and Two of the following: a. Positive brain MRI (nine T2 lesions or four or more T2 lesions with positive VEP) b. Positive spinal cord MRI (two focal T2 lesions) c. Positive CSF |

Appendix 2 New York Heart Association Functional Classification (1994)

| NYHA Class | Symptoms |
|---------------|---|
| I | No symptoms and no limitation in ordinary physical activity, e.g. shortness of breath when walking, climbing stairs etc. |
| II | Mild symptoms (mild shortness of breath and/or angina) and slight limitation during ordinary activity. |
| 111 | Marked limitation in activity due to symptoms, even during less-than-ordinary activity, e.g. walking short distances (20-100 m). Comfortable only at rest. |
| IV | Severe limitations. Experiences symptoms even while at rest. Mostly bedbound patients. |

Version 5

Appendix 3 Toxicity Grading Scale for Healthy Adult and Adolescent Volunteers Enrolled in Preventative Vaccine Clinical Trials

(Source: Guidance for Industry issued by U.S. DHHS September 2007)

The tables within the guidance document do not include a systemic line item for rigors/chills. Rigors/chills should be graded in accordance with the following scale:

| Systemic (General) | Mild (Grade 1) | Moderate (Grade 2) | Severe (Grade 3) | Potentially Life Threatening (Grade 4) |
|-----------------------|-------------------|---|--|--|
| Rigors/Chills | Mild | Mild to Moderate, no antipyretic medication (paracetamol/NSAID) indicated | Moderate, antipyretic or corticosteroid indicated | Severe, symptomatic >4 hours despite treatment with antipyretic /corticosteroid |

The systemic line item for pyrexia has been amended in line with existing guidelines for adverse events associated with oncology studies (ECOG (http://ecog.dfci.harvard.edu/general/ctc.pdf) and NHI CTEP

(http://ctep.cancer.gov/protocolDevelopment/electronic_applications/ctc.htm)).

| Systemic (General) | Mild (Grade 1) | Moderate (Grade 2) | Severe (Grade 3) | Potentially Life Threatening (Grade 4) |
|-----------------------|-------------------|-----------------------|---------------------------|---|
| Fever (°C) | 37.1 – 38.0 | 38.1 – 40 | >40 for less than 24 h | >40 for more than 24h despite prophylaxis or treatment with antipyretics (paracetamol or NSAID) |

[The Guidance for Industry document "Toxicity Grading Scale for Healthy Adult and Adolescent Volunteers Enrolled in Preventative Vaccine Clinical Trials" is presented in the companion Operations Manual]

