4.4 Dose Limiting Toxicity (DE phase only)

A DLT is a clinically significant adverse event (AE) or laboratory abnormality assessed by the Co-Principal Investigators as at least possibly related to the study drug and unrelated to disease progression, concurrent illness, or concomitant medications, occurring within Cycle 1. Toxicity will be graded and recorded according to the Toxicity Grading Scale for Healthy Adult and Adolescent Volunteers Enrolled in Preventative Vaccine Clinical Trials (presented in the companion Operations Manual), modified to include a systemic line item for rigors/chills and an amendment to the classification of pyrexia (Appendix 3). A DLT is defined as:

- Grade 3 or 4 adverse event, except for fatigue and fever and/or rigors/chills
- Grade 4, or an increase above baseline of 2 or more grades, fatigue
- Grade 4 fever and/or rigors/chills.

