12.2.5 Treatment of Adverse Events

AEs that may be related or possibly related to a drug with immune modulation mechanisms of action may include anaphylactic reaction or acute pro-inflammatory cytokine release.

- Management of anaphylaxis should follow appropriate guidelines and recommendation such as those made by the Resuscitation Council of New Zealand, 2006
- Acute pro-inflammation should be treated with appropriate fluid replacement, anti-inflammatory drugs (steroidal and non-steroidal) and antihistamines.

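### Appendix 3 ties Grade 4 fever and rigors, the only DLT grade for these events, to the treatment given, and leaves some severe reactions without a grade

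*Protocol*

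**What the plan says.** Section 4.4 of the Protocol (and the Synopsis) makes "Grade 3 or 4 adverse event, except for fatigue and fever and/or rigors/chills" a DLT. For fever and rigors/chills only the top grade counts: "Grade 4 fever and/or rigors/chills".

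Those grades come from Appendix 3. It supplies the only rigors scale, since it notes that the published guidance has no such line, and it replaces the guidance's fever line.

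- Rigors Grade 2: "Mild to Moderate, no antipyretic medication (paracetamol/NSAID) indicated".
- Rigors Grade 3, in a column headed Severe: "Moderate, antipyretic or corticosteroid indicated".
- Rigors Grade 4: "Severe, symptomatic >4 hours despite treatment with antipyretic /corticosteroid".
- Fever Grade 3: ">40 for less than 24 h".
- Fever Grade 4: ">40 for more than 24h despite prophylaxis or treatment with antipyretics (paracetamol or NSAID".

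On treatment, Section 12.2.5 states: "Acute pro-inflammation should be treated with appropriate fluid replacement, anti-inflammatory drugs (steroidal and non-steroidal) and antihistamines". Section 5.4 bars systemic corticosteroids during the study, but in the same section permits medication needed for adverse events.

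**The concern.** Fever and chills are the effect the sponsor expects from this drug; Section 2.1 bases the desirable dose range on them. They are therefore the events for which the DLT boundary most needs to be unambiguous.

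Two subjects with the same fever, above 40 °C for more than a day, can be classed differently. One given paracetamol has a Grade 4 event and, if it is judged at least possibly related, a DLT. One given only a corticosteroid has an event that fits no cell. Nothing in the Protocol says how an event without a grade enters the DLT count. Cohorts have three subjects, and the MTD becomes the recommended Phase 2 dose (Section 4.3), so a single classification can change the dose taken into the dose-confirmation phase.

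**Working it through.** **Step 1: apply the Appendix 3 cells literally.** The inputs are the two rows of Appendix 3 and the treatments named in Section 12.2.5. Each entry is the grade that the event matches.

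| Event | Untreated, or fluids/antihistamine only | Corticosteroid only | Paracetamol or NSAID |
|---|---|---|---|
| Fever >40 °C, <24 h | 3 | 3 | 3 |
| Fever >40 °C, >24 h | no cell | no cell | 4 (DLT grade) |
| Severe rigors, ≤4 h | no cell | no cell | no cell |
| Severe rigors, >4 h | no cell | 4 (DLT grade) | 4 (DLT grade) |

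The second and fourth rows are where treatment decides whether the DLT grade is reached. In the fever row the class of drug matters, because only paracetamol or an NSAID satisfies Grade 4. In the rigors row either class does, so what matters is whether one of them was given at all.

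The third row is a wording conflict. The Grade 3 cell says Moderate while its column says Severe, so a severe reaction of 4 h or less either has no cell or falls in Grade 3 by the column heading. It is not Grade 4 in either case, so it is not a DLT.

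Fever Grade 4 also mentions prophylaxis, but Section 4.7 describes antipyretic premedication for the dose-confirmation phase only, and DLTs apply to the dose-escalation phase only. The planned route to Grade 4 in dose escalation is therefore treatment.

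**Step 2: what one uncounted event does under Section 4.3.**

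- True 1 of 3, counted 0 of 3: expand to six becomes escalate.
- True 2 of 3, counted 1 of 3: stop becomes expand.
- True 2 of 6, counted 1 of 6: stop becomes escalate.

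**Step 3: reproduce the Protocol's operating characteristics.** With true DLT rate p, Section 4.3 gives

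P(escalate) = (1−p)³ + 3p(1−p)² × (1−p)³.

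- p = 0.10: 0.729 + 0.243 × 0.729 = 0.906
- p = 0.20: 0.512 + 0.384 × 0.512 = 0.709
- p = 0.30: 0.343 + 0.441 × 0.343 = 0.494
- p = 0.40: 0.216 + 0.432 × 0.216 = 0.309

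These match the 91%, 71%, 49% and 31% in Section 14.1, and the other five entries also reproduce. The table is right, but it assumes that every DLT is counted.

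**Step 4: sensitivity, on an assumption.** If a share f of all DLTs at a dose goes uncounted, the rate the rule sees is p(1−f). For p = 0.40 and f of 0, 25, 50 and 75%, that rate is 40, 30, 20 and 10%, and the escalation probability is 31, 49, 71 and 91%. The documents give no value for f. Only fever and rigors events in the empty cells can contribute to it; every other Grade 3 or 4 event still counts, fatigue under its own rule. The range shows that the rule is sensitive to undercounting. It is not an estimate for this trial.

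**The case against.** The strongest reply is that the empty cells will rarely be used. Section 12.2.5 says acute pro-inflammation should be treated, and taken as a whole its list includes a non-steroidal drug, which satisfies the fever cell. Subjects stay in the unit for 24 h after the first dose, with frequent vital signs. The expected reactions are Grade 1 to 2. The Safety Review Team includes an independent clinical expert and the Medical Monitor, works from all available safety data (Section 4.8), and drugs given for adverse events are recorded in the CRF.

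Much of that stands as an argument about frequency. But Section 12.2.5 fixes no combination or order of drugs, and after later doses subjects may leave the same afternoon, so an untreated or steroid-only course is possible. The Safety Review Team can look beyond the grade, but nothing in its remit supplies a missing one.

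Four stronger readings are tempting and are not supported:

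- *Choosing an antipyretic or a corticosteroid changes the rigors grade.* It does not; either satisfies Grade 4.
- *Early rescue that ends a fever before 24 h hides a DLT.* That event is Grade 3 whatever ended it. Objecting to this disputes the duration threshold the sponsor chose and identifies no gap.
- *Every gap errs toward not counting a DLT.* This is likely in practice but is not stated. A grader might use the Grade 4 column heading for an event that matches no cell.
- *The treating physician can steer the MTD.* The Co-Principal Investigators assess DLTs and sit on the Safety Review Team, but that they also choose the rescue is an inference.

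**Conclusion.** The point holds as a defect in the grading table. Fever above 40 °C for more than 24 h, untreated or given only a corticosteroid, has no grade. Nor do severe rigors beyond 4 h given neither an antipyretic nor a corticosteroid. The two rows name different drugs, and the Grade 3 rigors cell contradicts its heading, although that last conflict does not affect the DLT count.

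This rests on a literal reading of Appendix 3, and its consequence on the further assumption that an event without a grade would not be counted. On that assumption one event is enough to change a cohort decision. How often this would happen, and how far it would move the MTD, cannot be derived from the documents. A reader might take one escalation probability from the sensitivity range as the expected effect; no figure in the Protocol supports that. The correction is still worth making, because this table is the decision threshold for the MTD and the change is small.

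**What to change.** The sponsor and the Safety Review Team should reconcile the rigors and fever rows of Appendix 3 with each other and with Sections 4.4, 5.4 and 12.2.5. Each combination of severity, duration and treatment (none, antipyretic, corticosteroid, other measures) should fall in exactly one grade, the drug lists should agree, and the wording of the Grade 3 rigors cell should match its column. Which combinations are dose-limiting is for them to decide; no threshold or treatment is proposed here.

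At each cohort review, list every severe rigors event and every temperature above 40 °C with its duration and the rescue given, so that the escalation decision does not rest on the grade alone.

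The cost is one revised table and one short listing per cohort. The downside is that events in earlier cohorts may need re-grading.
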